7.1.4.3 Double-blind Maintenance Phase Week 13 (Visit 5.1)

Subjects and/or caregivers will collect UC-DAI symptoms (rectal bleeding and stool frequency) via e-diary and will complete the DUCS and the Overall Current Health e-diary once a day before bedtime for 5 days prior to each study visit in the Double-blind Maintenance Phase except for Visit 5, which includes collection and dispensation of investigational product only.

See [Table 3](#) for a listing of all Visit 5.1 procedures.

7.1.4.4 Double-blind Maintenance Phase Week 26/Withdrawal (Visit 5.2)

The Double-blind Maintenance Phase Withdrawal Visit may occur at any time the subject discontinues participation in the Double-blind Maintenance Phase, or at completion of the study at Week 26 of the Double-blind Maintenance Phase.

Collection of stool samples for all assessments must occur before administration of any bowel preparations for endoscopy if samples are collected on the same day as bowel preparation administration.

Endoscopy (flexible sigmoidoscopy or colonoscopy) should be performed at Visit 5.2 where possible. If performed, endoscopic videos or photographs will be collected and sent to the study's central endoscopy reader for evaluation of mucosal healing. Please see a description of criteria used for endoscopic scoring in [Appendix 2](#).

Subjects and/or caregivers will have collected UC-DAI symptoms (rectal bleeding and stool frequency) via e-diary once a day before bedtime for 5 days prior to each study visit in the Double-blind Maintenance Phase except for Visit 5, which includes collection and dispensation of investigational product only. The average stool frequency and rectal bleeding scores will be calculated and made available to the investigator through a report from the e-diary provider. The average stool frequency and rectal bleeding scores will be added to the PGA score determined by the investigator to calculate the partial UC-DAI. Please see a description of the PGA in Section [7.2.1.1](#) and the UC-DAI in Sections [7.2.1.1](#) and [7.2.1.2](#).

The IMPACT III (for children aged 8-17 years) and Global Change in Health questionnaires will be completed via paper at Visit 5.2. Please see a description IMPACT III and Global Change in Health questionnaires in Section [7.2.4.1](#).

The PUCAI score will be calculated by a physician at the site, where applicable. Please see a description of the PUCAI in Section [7.2.4.1](#).

A pharmacokinetic sample will be taken with the biochemistry and hematology sample from subjects at sites qualified for and participating in the pharmacokinetic sampling. Please see a description of the pharmacokinetic sampling in Section [7.2.3](#).

See [Table 3](#) for a listing of all Visit 5.2 procedures.

7.1.5 Follow-up Period (Visit 6)

The follow-up period for this protocol is 7 days following last dose of investigational product. All subjects, whether they have completed the study or withdrawn early, must have a follow-up contact.

At the end of this period there will be a visit or telephone call initiated by the site staff to query for SAEs, AEs, and concomitant treatments. All AEs and SAEs that are not resolved at the time of this contact will be followed to closure (see Section [8](#)).

7.1.6 Additional Care of Subjects After the Study

No additional care is planned after a subject's participation in this study unless required by local laws, ethics committees or competent authorities. The Principal Investigator at each site will be responsible for oversight of his or her study participant who continues on MMX mesalamine/mesalazine after study completion as a part of the aftercare program.

7.2 Study Evaluations and Procedures

7.2.1 Efficacy

The primary efficacy assessment of the Double-blind Acute Phase is the proportion of subjects with a clinical response (defined as partial UC-DAI ≤ 1 with rectal bleeding=0 **and** stool frequency ≤ 1 **and** PGA=0) at Week 8. The primary efficacy assessment of the Double-blind Maintenance Phase is the proportion of subjects with a clinical response at Week 26.

A secondary efficacy assessment of the Double-blind Acute Phase is the proportion of subjects with a clinical and endoscopic response at Week 8 defined as full UC-DAI ≤ 2 with rectal bleeding=0 **and** stool frequency ≤ 1 **and** PGA=0, **and** with mucosal healing (endoscopy score ≤ 1) based on central reading. In addition, there must be at least a 1-point reduction in endoscopy score from baseline. A secondary efficacy assessment of the Double-blind Maintenance Phase is the proportion of subjects with a clinical and endoscopic response at Week 26.

Further secondary assessments will explore the change in the DUCS and the percentage of subjects with an improvement in PUCAI from baseline to the end of the Double-blind Acute Phase. The change in DUCS will be explored from Week 0 to Week 26 of the Double-blind Maintenance Phase, and the percentage of subjects in remission using the PUCAI score at Week 26 of the Double-blind Maintenance Phase will also be explored.

7.2.1.1 Partial UC-DAI Score

The partial UC-DAI score is based on the individual parameters of the modified full UC-DAI without the endoscopic component. (Please see Section 7.2.1.2 for a description of the modified full UC-DAI.) It includes stool frequency, rectal bleeding, and PGA only. All 3 parameters will be assessed individually on a scale from 0-3; the maximum total partial UC-DAI score is 9.0.

Subjects' symptoms (rectal bleeding and stool frequency) will be reported by the subjects/caregivers in the e-diary once a day before bedtime starting from the evening of the Screening Visit (Visit 1) through the Baseline Visit (Visit 2). Subjects' symptoms are completed once a day before bedtime for the 5 days immediately prior to Visits 3, 3.1, and 3.2 of the Double-blind Acute Phase, Visits 4, 4.1, 4.2 of the Open-label Acute Phase and Visits 5.1 and 5.2 of the Double-blind Maintenance Phase. Symptom data should also be reported as soon as a subject's symptoms suggest that they might be experiencing an acute flare during the Double-blind Maintenance Phase, and they should contact the site to arrange for an unscheduled visit. In this case, symptoms should be entered for 5 days immediately prior to the unscheduled visit, if possible.

Stool frequency and rectal bleeding will be assessed on a scale from 0-3. Scores will be based on 1 of 2 versions of e-diary questions. One version is for children and adolescents aged 11-17 years and the other is for caregivers of children aged 5-10 years. Subject age at the beginning of their current study phase will determine which version of the e-diary will be completed for the entire phase; the version being completed will not change from caregiver to subject completion during a phase. However, the version should change from caregiver completion to subject completion for the next phase, if applicable based on a subject's age change.

Questions and responses for children and adolescents aged 11-17 years:

How many more times did you poop than you normally do since you went to bed last night?

- I didn't poop more than I normally do
- I pooped 1 or 2 more times than normal
- I pooped 3 or 4 more times than normal
- I pooped 5 or more times than normal.

Did you have blood in your poop?

- I didn't see any blood in my poop
- I saw streaks of blood (a small amount) in my poop
- I saw some blood (more than a small amount) in my poop
- I saw mostly blood (a lot) in my poop.

Questions and responses for caregivers of children aged 5-10 years:

Based on what you observed, how many more times did your child have a bowel movement than they normally do since they went to bed last night?

- They didn't have more bowel movements than they normally do
- They had 1 or 2 more bowel movements than normal
- They had 3 or 4 more bowel movements than normal
- They had 5 or more bowel movements than normal.

Based on what you observed, did your child have blood in their stool?

- I didn't see any blood in my child's stool
- I saw streaks of blood (a small amount) in my child's stool
- I saw some blood (more than a small amount) in my child's stool
- I saw mostly blood (a lot) in my child's stool.

For determination of the partial UC-DAI, the average of the symptom scores of the last available 3 days within the 5-day period immediately prior to the study visit will be used. No symptom data older than 5 days prior to the study visit will be used. Data collected on days when bowel preparations have been administered or when endoscopy has been performed will be excluded.

Approximately 4 to 7 days prior to the Baseline Visit (Visit 2) and prior to each subsequent visit, it is recommended that site staff telephone the subject or the subject's caregiver to remind them to enter UC-DAI symptoms (rectal bleeding and stool frequency) into the e-diary every night, even if the subject has no symptoms. A missed day's data may be entered until 12:00 hours the following day.

A minimum of 1 score each for stool frequency and rectal bleeding must be available in order to randomize subjects into either the Double-blind Acute Phase or the Double-blind Maintenance Phase. If no data are available, the average value will be considered missing and the subject will be considered a screen failure.

Calculations of average stool frequency and rectal bleeding scores will proceed as follows:

- If symptom scores from the last 3 days are available, average = $(x_1+x_2+x_3)/3$; the average value should be rounded up to 1 decimal place:
 - For example: $(0+1+0)/3 = 0.3333$; value = 0.3; $(1+0+1)/3=0.666666$; value=0.7; $(2+2+2)/3=2.0$
- If symptom scores from the last 2 days are available, average = $(x_1+x_2)/2$; the average value should be rounded up to 1 decimal place.
- If symptom scores from only 1 day are available, average = $(x_1/1) = x_1$.

The PGA will be performed at all visits where the partial UC-DAI score is calculated by the study site, and is scored on a scale from 0-3, where 0=no active disease, 1=mild disease, 2=moderate disease, and 3=severe disease. The PGA should be performed by the same investigator at all visits, if possible, for consistency in evaluation.

Scoring of the PGA by the investigator should take into account the following parameters:

- Rectal bleeding
- Stool frequency and consistency
- Night-time bowel movements
- Abdominal pain
- Impact to daily activities
- Physical findings
- Endoscopic findings (if endoscopy is performed).

The PGA is to be recorded in source documentation and added to the average stool frequency and average rectal bleeding scores to calculate the partial UC-DAI score. Sites should not perform rounding of partial UC-DAI scores. The average stool frequency and rectal bleeding scores will be calculated and available to the investigator through a report from the e-diary provider.

7.2.1.2 Modified Full UC-DAI Score

The full UC-DAI is widely used to assess treatment efficacy in subjects with mild to moderate UC (Schroeder et al. 1987; Sutherland et al. 1987). It consists of 4 individual parameters: stool frequency, rectal bleeding, endoscopy score (mucosal appearance), and PGA. For the purpose of this study, the standard UC-DAI scale has been modified so that an endoscopy score of mild disease does not include friability; instead, friability will be scored as 2: moderate disease.

Please see a description of stool frequency, rectal bleeding and PGA in Section [7.2.1.1](#).

All 4 parameters will be assessed individually on a scale from 0-3; the maximum total modified full UC-DAI score is 12.0. The modified full UC-DAI score will be calculated at Baseline (Visit 2), Week 8 of the Double-blind Acute Phase (Withdrawal) for subjects not entering into the Open-label Acute Phase, Week 8 of the Open-label Acute Phase (Withdrawal) for subjects who have not had endoscopy at the end of the Double-blind Acute Phase, and Week 26 of the Double-blind Maintenance Phase (Withdrawal) visits. The total score will be calculated by summing the individual scores for the 4 parameters (endoscopy score will be based on the central reader's score). The site is not required to calculate the full UC-DAI; this will be calculated centrally using e-diary and eCRF data.

For determination of the modified full UC-DAI, the average of the symptom scores of the last available 3 days within the 5-day period immediately prior to study visits where endoscopic data are available, will be used. No symptom data older than 5 days prior to the study visit will be used. Data collected on days when bowel preparations have been administered or when endoscopy has been performed will be excluded.

An endoscopy must be performed and mucosal appearance scored within 21 days prior to the Screening Visit (Visit 1), during the Screening period or at the Baseline Visit (Visit 2) depending on the subject's UC history and phase of the study into which they are entering. All efforts should be made to perform endoscopy at Week 8 of the Double-blind Acute Phase (or Week 8 of the Open-label Acute Phase, as applicable), Week 26 of the Double-blind Maintenance Phase, or the subject's withdrawal if different from these visits.

During this study, an attempt will be made to collect endoscopy data in approximately 30% of subjects at the end of the Acute Phase (combined Double-blind and Open-label) and approximately 30% at the end of the Double-blind Maintenance Phase. In addition, data from endoscopies performed as a part of routine clinical care during a subject's participation in the study will be collected.

Endoscopies will be centrally read and scored for this study, and endoscopic video or photographs must be provided to the central reader for each endoscopy performed. Video images are preferred; however, photographic images will be accepted when video images are not of sufficient quality, as determined by the central reader during individual site image evaluation prior to enrollment at the site. Further details of requirements for video and photographic images will be provided to study sites under separate cover by the central reader. All endoscopies should be performed by the same investigator/endoscopist, if possible, to ensure consistency in endoscopy.

Please see [Appendix 2](#) for the modified full UC-DAI.

7.2.2 Safety

The name and address of each third party vendor (eg, clinical laboratory) used in this study will be maintained in the investigator's and sponsor's files.

7.2.2.1 Medical and Medication History

At screening, the subject's medical history (including UC history) and concomitant medications will be reviewed. Investigator site staff will conduct this review via interview with the subject and/or caregiver to determine eligibility. Any new medical events or changes in intensity from the Screening Visit (Visit 1) noted during the study should be evaluated for report as an AE (see Section 8). New medications or changes to existing medications must be added or updated as appropriate.

7.2.2.2 Physical Examination

Abnormalities identified at the Screening Visit (Visit 1) will be documented in the subject's source documents. Changes after the Screening Visit (Visit 1) will be captured as AEs, as deemed appropriate by the investigator.

7.2.2.3 Height and Weight

Height will be assessed at the Screening Visit (Visit 1) and at the final visit of each phase. Weight will be assessed at the Screening Visit (Visit 1), the Baseline Visit (Visit 2) and at the final visit of each phase.

The collection of height and weight data should be precise. A calibrated stadiometer must be used for all height measurements. Height should be measured in stocking feet (without shoes) with the subject standing on a flat surface and with chin parallel to the floor. The body should be straight but not rigid. The subject's height should be recorded to the nearest 0.5 inch or 1 cm.

The same calibrated scale must be used for all weight measurements. Weight should be measured in stocking feet (without shoes) and recorded to the nearest 0.2 kg.

7.2.2.4 Adverse Event Collection

At each study visit, subjects will be questioned in a general way to ascertain if AEs have occurred since the previous visit (eg, "Have you had any health problems since your last visit?"). Adverse events are collected from the time informed consent is signed. (Please refer to Section 8, Adverse and Serious Adverse Events Assessment.)

In addition, any symptoms/conditions reported during assessments or collected via structured data collection will be evaluated by the investigator at each study visit to determine whether these are AEs.

7.2.2.5 Vital Signs

Vital signs include blood pressure and pulse. Blood pressure should be determined by cuff (using the same method, the same arm, and in the same position throughout the study). Any clinically significant deviations from the Baseline Visit (Visit 2) vital signs which are deemed clinically significant in the opinion of the investigator are to be recorded as an AE.

Measurements of vital signs (blood pressure and pulse) will be performed at all study visits. Blood pressure and pulse will be determined in the sitting position (after 5 minutes).

7.2.2.6 Clinical Laboratory Evaluations

All clinical laboratory assays will be performed according to the laboratory's normal procedures. Reference ranges are to be supplied by the laboratory and will be used to assess the clinical laboratory data for clinical significance and out-of-range pathological changes. The investigator should assess out-of-range clinical laboratory values for clinical significance, indicating if the value(s) is/are not clinically significant or clinically significant. Abnormal clinical laboratory values, which are unexpected or not explained by the subject's clinical condition, may, at the discretion of the investigator or sponsor, be repeated as soon as possible until confirmed, explained, or resolved.

The following routine clinical laboratory assessments will be performed (see Section 8.1.5 for additional clinical laboratory assessments that may be performed in the case of elevated liver enzymes):

Biochemistry (approximately 5mL sample)

Alanine aminotransferase	Direct bilirubin
Albumin	Gamma-glutamyl transferase
Alkaline phosphatase	Glucose random, serum
Aspartate aminotransferase	Lactate dehydrogenase
Bilirubin, total	Magnesium
Bicarbonate	Phosphate
Calcium	Potassium
Chloride	Sodium
Cholesterol, total	Total protein
Creatinine, enzymatic	Triglycerides
Creatine kinase	Urea (blood urea nitrogen)
C-reactive protein standard	Uric acid

Hematology (approximately 3mL sample)

Complete blood count (red blood cells, white blood cells, platelets, hemoglobin)	White blood cell differential
Hematocrit	

Urinalysis

pH	Ketones
Specific gravity	Bilirubin
Protein	Blood
Glucose	

Microscopic examination will be conducted if protein and/or blood is/are detected during urinalysis. The microscopic examination will consist of red blood cells, white blood cells, casts, and bacteria.

Please see [Table 1](#), [Table 2](#), and [Table 3](#) for visits requiring biochemistry, hematology and urinalysis collection.

7.2.2.7 Pregnancy Test

A serum β -HCG pregnancy test is performed for all females of childbearing potential at the following visits as applicable to the subject's participation in the study:

- Screening Visit (Visit 1)
- Double-blind Acute Phase: Week 8 (Visit 3.2)
- Open-label Acute Phase: Week 8 (Visit 4.2)
- Double-blind Maintenance Phase: Week 26 (Visit 5.2)
- If pregnancy is suspected
- On withdrawal of the subject from the study.

A urine pregnancy test is performed for all females of childbearing potential at all other visits as indicated in [Table 1](#), [Table 2](#), and [Table 3](#).

7.2.2.8 Stool Assessment

Collection of stool samples for all assessments must occur before administration of any bowel preparations for endoscopy if samples are collected on the same day as bowel preparation administration.

If a standard of care stool sample has been collected within 24 hours prior to the Screening Visit (Visit 1), this sample may be used for screening assessments and evaluations provided that written informed consent/assent has been collected before the stool is sent for laboratory analysis.

Screening Assessments

A stool sample will be collected during the Screening Visit (Visit 1), which is a period of 3 to 21 days. If a standard of care stool sample was collected within 24 hours prior to the Screening Visit (Visit1), this sample may be used for screening assessments and evaluations. The sample must be collected in sufficient time to ensure results reporting within the Screening Visit (Visit 1) period. Stool samples collected for culture may be processed by local laboratories; however, results from the central laboratory analysis will prevail and will be entered into the eCRF. The following parameters will be assessed:

- Culture for enteric pathogens including *Salmonella*, *Shigella*, *Yersinia*, *Aeromonas*, *Plesiomonas*, and *Campylobacter*

- Presence of *Clostridium difficile* toxin
- Microscopic examination of stool for ova and parasites.

If the stool sample is positive for any of the above parameters, the subject will not be eligible for the study (see Section 4.2).

[REDACTED]

[REDACTED]

[REDACTED]

[REDACTED]

[REDACTED]

[REDACTED]

[REDACTED]

[REDACTED]

7.2.3 Pharmacokinetic Procedures

7.2.3.1 Blood Sample Collection and Handling Procedures

Blood samples will be collected at the times specified in [Table 1](#), [Table 2](#) and [Table 3](#) to allow measurement of plasma concentrations of 5-ASA and its major metabolite Ac-5-ASA. Pharmacokinetic sampling will occur only at participating sites that have been appropriately assessed and qualified for pharmacokinetic sampling.

The date and time of last dose of investigational product and date and time of pharmacokinetic sampling will be collected.

Venous blood samples (2mL) will be drawn by direct venipuncture into lithium heparin Vacutainer® tubes, capped and mixed by inversion (x3) and chilled immediately on crushed ice.

Blood samples (2mL/sample) may be collected at Visits 3.2/Withdrawal, 4.2/Withdrawal and 5.2/Withdrawal.

Within 15 minutes following each sample collection, the blood tubes will be centrifuged at approximately 2000 x g (15 minutes, 4°C). The separated plasma will be decanted into 2 clearly labeled polypropylene tubes (0.4mL of plasma in the primary tube and in the backup tube) via a plastic pipette. All samples must be stored nominally at -80°C and the freezer temperature will be controlled, monitored and recorded during the storage period until the samples are shipped to the central laboratory. The study monitor must be notified of any temperature excursions.

Plasma sample tubes for bioanalysis must be freezer safe and identified with freezer safe labels provided by the Sponsor. The labels will contain the following information:

- Study Number
- Visit (Visit 3.2/Withdrawal, Visit 4.2/Withdrawal, 5.2/Withdrawal)
- Subject Identifier
- Matrix Identifier (plasma)
- Split (primary or backup tube).

There will be up to 3 blood samples collected for pharmacokinetic bioanalysis per subject during the study.

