4.5 Discontinuation of Subjects

A subject may withdraw from the study at any time for any reason without prejudice to their future medical care by the physician or at the institution. The investigator or sponsor may withdraw the subject at any time (eg, in the interest of subject safety). The investigator is encouraged to discuss withdrawal of a subject from investigational product with the medical monitor when possible.

If investigational product is discontinued, regardless of the reason, the evaluations listed for the Withdrawal Visit (Visits 3.2, 4.2, or 5.2, depending on the phase) are to be performed as completely as possible. Whenever possible, all discontinued subjects should also undergo the protocol-specified follow-up. Comments (spontaneous or elicited) or complaints made by the subject must be recorded in the source documents. The reason for termination, date of stopping investigational product, and the total amount of investigational product taken must be recorded in source documents.

Subjects who discontinue will not be replaced.

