6.2.3 Dosing

Subjects entering the Double-blind Acute Phase or entering the Double-blind Maintenance Phase directly will be randomized to low- or high-dose MMX mesalamine/mesalazine stratified by their weight group at the Baseline Visit (Visit 2).

Subjects entering the Double-blind Maintenance Phase after completing 1 or both of the Acute Phases will be re-randomized to low- or high-dose MMX mesalamine/mesalazine at the start of the Double-blind Maintenance Phase at Visit 3.2 (Week 8 of the Double-blind Acute Phase) or 4.2 (Week 8 of the Open-label Acute Phase), as applicable, based on their weight at the time of re-randomization.

Doses will be as follows:

- 900 or 1800mg/day for subjects weighing 18 to \leq 23kg
- 1200 or 2400mg/day for subjects weighing >23 to \leq 35kg
- 1800 or 3600mg/day for subjects weighing >35 to \leq 50kg
- 2400 or 4800mg/day for subjects weighing >50 to \leq 90kg.

Subjects participating in the Open-label Acute Phase will receive the high dose for their weight group. The subject's weight at Visit 3.2 (Week 8/Withdrawal of the Double-blind Acute Phase) will be used to determine the high dose assigned to the subject.

Investigational product will be administered orally, once daily, in accordance with the MMX Mesalazine (Mesalamine) Investigator's Brochure. No titration or dose adjustment is allowed.

Dosing with investigational product will begin the day of the Baseline Visit (Visit 2) if the subject's currently prescribed 5-ASA treatment (if applicable) has not yet been taken that day. If the subject's currently prescribed 5-ASA treatment (if applicable) has been taken the day of the Baseline Visit (Visit 2), dosing with investigational product will begin the day after the Baseline Visit (Visit 2).

When proceeding through study phases, dosing with newly prescribed investigational product will begin the day of the study visit if the subject's currently prescribed investigational product from the current phase has not yet been taken that day. If the subject's currently prescribed investigational treatment has been taken the day of the study visit, dosing with newly prescribed investigational product will begin the day after the first study visit of the new phase.

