The IMPACT III (for children aged 8-17 years) and Global Change in Health questionnaires will be completed via paper at Visit 3.2. Please see a description IMPACT III and Global Change in Health questionnaires in Section [7.2.4.1](#).

The PUCAI score will be calculated by a physician at the site, where applicable. Please see a description of the PUCAI in Section [7.2.4.1](#).

A pharmacokinetic sample will be taken with the biochemistry and hematology sample from subjects at sites qualified for and participating in the pharmacokinetic sampling. Please see a description of the pharmacokinetic sampling in Section [7.2.3](#).

See [Table 1](#) for a listing of all Visit 3.2 procedures.

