5.10 Analysis of Pharmacokinetic Data

Blood samples will be collected for determination of 5-ASA and Ac-5-ASA plasma concentrations, and the plasma samples will be assayed for 5-ASA and Ac-5-ASA using validated analytical methods.

Plasma concentrations reported as BLQ (below the limit of quantification) of the assay will be reported as zero on the data listings, and BLQ concentrations are treated as zero in the calculation of summary statistics.

The plasma concentrations of 5-ASA and Ac-5-ASA will be summarized by treatment and visit using descriptive statistics (number of observations, mean, standard deviation, coefficient of variation, median, Q1, Q3, maximum, and minimum) using the Safety Analysis Set for each study phase.

A population pharmacokinetic model was developed based on the 5-ASA and Ac-5-ASA plasma concentration data (full pharmacokinetic profiles) from SPD476-112. The plasma concentration data from this study (sparse pharmacokinetic sampling) will be pooled with the plasma concentration data from SPD476-112 to update the original population pharmacokinetic analysis. The population pharmacokinetic methods will be described in a separate document from this statistical analysis plan.

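### The plasma concentration tables ignore the recorded time since last dose and do not separate early-withdrawal samples, so arm means and CVs can mix on-drug, off-drug, pre-dose and post-dose values

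*Protocol*

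**What the plan says.** **Collection.** Protocol 7.2.3.1 plans one sample per phase: "Blood samples (2mL/sample) may be collected at Visits 3.2/Withdrawal, 4.2/Withdrawal and 5.2/Withdrawal". Each of these visits is both the end-of-phase visit and the withdrawal visit, and the tube label carries that combined name. The same section says that "The date and time of last dose of investigational product and date and time of pharmacokinetic sampling will be collected".

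**Timing of the draw.** No time relative to dose is set. Protocol 7.1.2.3 says "A pharmacokinetic sample will be taken with the biochemistry and hematology sample from subjects at sites qualified for and participating" in PK sampling, and 7.1.3.3 and 7.1.4.4 do the same for the other phases. For a move between phases, Protocol 6.2.3 provides both for the case where the subject's "currently prescribed investigational treatment has been taken the day of the study visit" and for the case where it has not.

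**After stopping drug.** Protocol 4.5 begins "If investigational product is discontinued, regardless of the reason, the evaluations listed for the Withdrawal Visit" and asks for these evaluations to be done as fully as they can be. It gives no maximum interval from the last dose.

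**Analysis.** SAP 5.10: "The plasma concentrations of 5-ASA and Ac-5-ASA will be summarized by treatment and visit using descriptive statistics". The statistics are n, mean, SD, CV, median, quartiles and range, on the Safety Analysis Set of each phase, which requires only one dose in that phase. It adds that "BLQ concentrations are treated as zero in the calculation of summary statistics". The titles of Tables 14.2.3.1.1 to 14.2.3.1.3 name phase and arm only. Draw times appear in Listing 16.2.5.4.

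**Population PK.** SAP 5.10 also pools these sparse data with those of SPD476-112 to update a population model, whose methods are in a separate document.

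**The concern.** A plasma concentration cannot be interpreted without knowing how long after the dose it was taken. SAP 5.10 has that information available and does not use it in the tables. Two mixtures can follow.

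- *Off-drug samples.* A child who stopped drug some days before the withdrawal visit may give a sample below the limit of quantification. It enters the arm mean as zero under the same visit label as a Week 8 or Week 26 sample.
- *Pre-dose and post-dose samples.* Some children will have taken that day's dose before the draw and others not. These values are averaged together.

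The study is meant to help choose paediatric doses (Protocol 2.1, SAP 1.2). A reader of these tables would naturally take the arm means as exposure on that arm's dosing, when they may partly reflect when blood was drawn and who had already stopped.

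**Working it through.** The documents give no sample size, precision or expected concentration for PK, so there is no stated figure to reproduce. The check has two parts.

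**1. Is there a rule that separates the samples?**

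| Element | Where | Rule found |
|---|---|---|
| Draw time relative to dose | Protocol 7.1.2.3, 7.1.3.3, 7.1.4.4, 7.2.3.1 | None; drawn with safety bloods |
| Day's dose taken before the visit or not | Protocol 6.2.3 | Both cases foreseen |
| Maximum gap from last dose to withdrawal sample | Protocol 4.5 | None |
| Withdrawal separated from Week 8 or 26 | Protocol 7.2.3.1, SAP 5.10 | No; one visit label |
| On-treatment requirement for PK summaries | SAP 5.10 | None |
| Time since dose in the summary | SAP 5.10, table titles | None |

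For comparison, SAP 5.9 defines the final on-treatment safety assessment as one made while the subject was still receiving product. The idea is already in the SAP but is not applied to PK.

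**2. How would the mixtures act?** All inputs here are assumptions; none is in the documents.

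*Zeros.* Let a share f of an arm's samples be zero, and let the on-drug samples have mean m and coefficient of variation c.

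- Mean in the table = (1 − f) × m. For f = 5%, 10%, 20%, 30% the multiplier is 0.95, 0.90, 0.80, 0.70.
- CV in the table = √[(1 + c²)/(1 − f) − 1]. With c = 0.60, so 1 + c² = 1.36:
  - f = 10%: √(1.36/0.90 − 1) = 0.715
  - f = 20%: √(1.36/0.80 − 1) = 0.837
  - f = 30%: √(1.36/0.70 − 1) = 0.971

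*Comparing arms by eye.* The high dose is twice the low dose in every weight group. Assume that the true ratio of mean concentrations is also 2.0. The ratio read from the table is then 2 × (1 − f_high)/(1 − f_low).

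- 20% zeros low, 5% high: 2 × 0.95/0.80 = 2.375
- 5% low, 20% high: 2 × 0.80/0.95 = 1.68
- 10% in both: 2.00, with both means 10% low

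*Mixed draw times.* Assume that a post-dose value is twice a trough value, and that p_low and p_high are the shares of post-dose draws. The ratio is 2 × (1 + p_high)/(1 + p_low).

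- p_low = 30%, p_high = 70%: 2 × 1.7/1.3 = 2.62
- Shares reversed: 2 × 1.3/1.7 = 1.53

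The distortion can go either way or cancel between the arms. Nothing in the documents says which.

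**The case against.** The case for leaving the plan alone is substantial.

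- *Dose and exposure have another analysis.* SAP 5.10 treats these as sparse samples for a population model, and recorded dosing and sampling times suit that use. A reader might infer that the times go unused altogether, or that these tables are the trial's main account of exposure by dose. The documents support neither: the model may use the times, and draw times are listed. The tables remain as described.
- *No comparison is planned.* The SAP specifies no high-to-low ratio and no PK test. This stands; the ratios above are ones that a reader would have to form.
- *Off-drug samples may be few.* Early leavers without benefit may, if eligible, go from Visit 3.2 to open-label treatment, with new product starting that day or the next (Protocol 6.2.3, 7.1.3). They need have no gap. Sampling is optional in wording and limited to participating sites. This stands for off-drug zeros but does not touch mixed draw times.
- *Medians and quartiles are also reported.* They resist a few zeros, and the minimum would show one. They do not say whether a zero was off drug, and they do not correct mixed draw times.
- *Some text cannot be seen.* The exploratory PK endpoint is redacted, and table specifications are in a separate document (SAP 1.1). A time rule there cannot be excluded; SAP 5.10 states none.

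**Conclusion.** The point holds as a minor one. Followed as written, SAP 5.10 allows off-drug samples, if there are any, and mixed pre-dose and post-dose samples into each arm's mean, SD and CV, although the data needed to separate them are collected. Only exploratory descriptive tables are affected; no efficacy or safety analysis depends on them.

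The size is unknown. The illustrative figures rest on assumed shares of zeros, an assumed CV of 60%, an assumed post-dose to trough ratio and an assumed true ratio of 2.0.

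Two stronger readings should be resisted. A reader might infer that the apparent high-to-low exposure ratio will be inflated; the arithmetic gives values above and below the true one, and the documents do not indicate which arm would have more off-drug or post-dose samples. A reader might also apply a half-life to claim a many-fold gap between early and late draws. Neither document gives a half-life, and Protocol 1.2 describes delayed and prolonged release, so a simple decline from shortly after dosing is not supported.

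**What to change.** In SAP 5.10, and in the specifications for Tables 14.2.3.1.1 to 14.2.3.1.3:

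1. Derive time since last dose for every sample from the recorded dates and times.
2. Restrict the summary tables to samples taken on treatment, within an interval from the last dose that is fixed before unblinding. The interval can be chosen without sight of the concentrations.
3. List later samples separately, with time since last dose, and exclude them from the means and CVs.
4. Add a plot of concentration against time since last dose, by arm.

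A pre-dose/post-dose split is optional where numbers allow. Finer time bins are not advised. Even if all 53 acute-phase subjects (SAP 3.1) were sampled, two arms by three bins would average about 9 per cell (53/6 = 8.8), each still mixing up to four weight-based dose levels, and sampling takes place only at participating sites.

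The cost is one derived variable, a few lines of SAP text and one figure. No new samples or data are needed. The downside is slightly fewer samples in the tables.
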